5.5.1. Withdrawal from the Study

Subjects who have withdrawn from the study should complete assessments for the Early Withdrawal Visit, 4 weeks after the last dose of mepolizumab (see Time and Events Table, Section 7.1).

A reason for the withdrawal from the study must be captured in the eCRF.

A subject must be discontinued if any of the following criteria are met:

- Withdrawal of consent
- Lost to follow-up

A subject will also be withdrawn from the study, in consultation with the medical monitor and principal investigator, if any of the following stopping criteria are met:

- Laboratory parameters: Clinically important changes in laboratory parameters identified.
- ECG: Clinically significant abnormality identified during the study that meet the QTc stopping criteria described in Section 5.5.3.
- Liver Chemistry: Meets any of the Liver chemistry stopping criteria (See Section 5.5.2 and Appendix 4.
- Pregnancy: Positive pregnancy test (see Appendix 3). Pregnancy and pregnancy outcomes of subjects exposed to mepolizumab will be followed.

The following actions must be taken in relation to a subject who fails to attend the clinic for a required study visit:

- The site must attempt to contact the subject and re-schedule the missed visit as soon as possible.
- The site must counsel the subject on the importance of maintaining the assigned visit schedule and ascertain whether or not the subject wishes to and/or should continue in the study.
- In cases where the subject is deemed 'lost to follow up', the investigator or designee must make every effort to regain contact with the subject (where possible, 3 telephone calls and if necessary a certified letter to the subject's last known mailing address or local equivalent methods). These contact attempts should be documented in the subject's medical record.

[figure not shown]
- Should the subject continue to be unreachable, only then will he/she be considered to have withdrawn from the study with a primary reason of “Lost to Follow-up”.

5.5.2. Liver Chemistry Stopping Criteria

[figure not shown]
Liver chemistry stopping and increased monitoring criteria have been designed to assure subject safety and evaluate liver event etiology (in alignment with the Food and Drug Administration [FDA] premarketing clinical liver safety guidance).

<http://www.fda.gov/downloads/Drugs/GuidanceComplianceRegulatoryInformation/Guidances/UCM174090.pdf>

Liver Chemistry Stopping and Increased Monitoring Algorithm

Liver Chemistry Increased Monitoring Algorithm with Continued Therapy for ALT $\geq 3xULN$ but $< 8xULN$

Required actions and follow-up assessment for all subjects who meet liver chemistry stopping or monitoring criteria are defined in [Appendix 4](#).

5.5.2.1. Study Treatment Restart or Rechallenge

Study treatment restart or rechallenge after liver chemistry stopping criteria are met, by any subject participating in this study, is not allowed.

5.5.3. QTc Stopping Criteria

- The *same* QT correction formula *must* be used for *each individual subject* to determine eligibility for and discontinuation from the study. This formula may not be changed or substituted once the subject has been enrolled. For example, if a subject is eligible for the protocol based on QT interval corrected for heart rate by Bazett's formula (QTcB), then QTcB must be used for discontinuation of this individual subject as well.
- Once the QT correction formula has been chosen for a subject's eligibility, the *same formula* must continue to be used for that subject *for all QTc data being collected for data analysis*. Safety ECGs and other non-protocol specified ECGs are an exception.
- The QTc should be based on single or averaged QTc values of triplicate electrocardiograms obtained over a brief (e.g., 5-10 minute) recording period. For example if a routine ECG demonstrates a prolonged QT, obtain 2 more ECGs

over a brief period and then use the averaged QTc values of the 3 ECGs to determine whether patient should be withdrawn from the study.

A subject who meets either of the bulleted criteria below will be withdrawn from the study:

- QTc >500 msec OR Uncorrected QT >600 msec
- Change from baseline (Visit 2) of QTc >60 msec

For patients with underlying **bundle branch block**, follow the discontinuation criteria listed below:

Baseline (Visit 2) QTc with Bundle Branch Block	Discontinuation QTc with Bundle Branch Block
<450 msec	>500 msec
450 – 480 msec	≥530 msec

5.6. Subject and Study Completion

A completed subject is one who has completed the End of Study (Week 12) visit.

The end of the study is defined as the last subject's last visit.

6. STUDY TREATMENT

6.1. Investigational Product and Other Study Treatment

The term 'study treatment' is used throughout the protocol to describe the mepolizumab drug product in safety syringe received by the subject as per the protocol design.

Mepolizumab liquid drug product will be supplied by GSK in Type I glass syringes with staked needles (1/2 inch x 29 gauge thin wall), sealed with latex-free rubber plungers. These will be assembled in single use, disposable safety syringes to enable delivery of the drug product. Each device will deliver 100mg mepolizumab in 1.0mL. The formulation contains sodium phosphate, citric acid, sucrose, EDTA and polysorbate 80.

	Study Treatment
Product name:	Mepolizumab (NUCALA) (SB240563)
Device:	Pre-filled syringe contained within a safety syringe
Formulation description:	100 mg/mL mepolizumab with sodium phosphate, citric acid, sucrose EDTA and polysorbate 80
Dosage form:	Sterile, liquid formulation
Unit dose strength(s)/Dosage level(s):	100 mg/mL; 1.0mL (deliverable)
Route of Administration	SC injection
Dosing instructions:	SC dose in thigh, abdomen or upper arm every 4 weeks
Physical description: mepolizumab	Clear to opalescent, colourless to pale yellow sterile solution for SC injection in a single-use, pre-filled syringe contained within safety syringe
Physical description of injection device:	Single use, disposable safety syringe assembled with the pre-filled syringe containing the drug product. The safety syringe enables delivery of the drug product by the subject/caregiver. A plastic needle cover shields the needle after injection to minimise the potential for needle stick injuries.
Manufacturer/source of procurement:	
Pre-filled syringe: Pre-filled syringe components are procured from Becton Dickinson. Prefilled syringe is filled with drug product and assembled at GSK, Barnard Castle, UK.
 
Safety syringe: The safety syringe components are manufactured by Becton Dickinson and assembled with the prefilled syringe at GSK, Barnard Castle, UK.

6.2. Medical Devices

The GSK manufactured medical devices (or devices manufactured for GSK by a third party) provided for use in this study are injection devices: a prefilled syringe contained within a safety syringe. The devices used in the study are representative of the devices planned to be marketed for the product.

The components that comprise the prefilled syringe, including glass barrel with prestaked needle and plunger are sourced from Becton Dickinson. The prefilled syringe is filled and assembled at GSK, Barnard Castle.

The safety syringe components are manufactured by Becton Dickinson. The safety syringe components are assembled with the prefilled syringe at GSK, Barnard Castle.

The IFU of these injection devices are provided in the SRM. The instructions were developed and optimised as a result of formative human factors studies and are representative of those that are planned for the product.

GSK medical device incidents, including those resulting from malfunctions of the device, must be detected, documented, and reported by the investigator throughout the study – see Section 7.7.3.

6.3. Treatment Assignment

All subjects will be assigned to the same treatment at Visit 2 (Week 0).

6.4. Blinding

This will be an open-label, single arm study.

6.5. Packaging and Labeling

The contents of the label will be in accordance with all applicable regulatory requirements.

6.6. Preparation/Handling/Storage/Accountability

No special preparation of study treatment is required.

Study treatment must be dispensed or administered according to procedures described herein. Only subjects enrolled in the study may receive study treatment. Only authorised site staff may supply study treatment. All study treatment must be stored in a secure area with access limited to the investigator and authorised site staff.

Mepolizumab will be supplied in a single-use safety syringe and should be stored in a refrigerator at 2 to 8°C with protection from light. Each injection device will contain 100 mg mepolizumab as a single 1.0 mL injection of the liquid drug product (100 mg/mL). Maintenance of a temperature log at the clinical dispensing sites (manual or automated) is required.

- The investigator or designee must confirm appropriate temperature conditions have been maintained during transit for all study treatment received and any discrepancies are reported and resolved before use of the study treatment.
- Only the subject or previously identified caregiver may administer the study treatment. Whilst on site, all study treatments must be stored in a secure environmentally controlled and monitored (manual or automated) area in accordance with the labelled storage conditions with access limited to the investigator and authorised site staff.
- The investigator, institution, or the head of the medical institution (where applicable) is responsible for study treatment accountability, reconciliation, and record maintenance (i.e. receipt, reconciliation and final disposition records).
- Further guidance and information for final disposition of unused study treatment are provided in the SRM.
- Under normal conditions of handling and administration, study treatment is not expected to pose significant safety risks to site staff.

- A Material Safety Data Sheet (MSDS)/equivalent document describing occupational hazards and recommended handling precautions either will be provided to the investigator, where this is required by local laws, or is available upon request from GSK.
- Subjects will be provided a safety syringe for home use at Visit 3 and asked to follow the information on the IFU with regards to the storage and use of the device. Cool bags and cold packs will be provided to transport the safety syringe from site to home. Subjects will be asked to return the used safety syringe at Visit 4. A record of the dispensing of the safety syringe given to the subject at Visit 3 and collection of the safety syringe returned at Visit 4 will be maintained by the Investigator or designee. The Investigator or designee will also inspect the returned safety syringe to determine if the dose has been dispensed correctly.

6.7. Training Session

Training of study treatment, handling and administration techniques by qualified study site personnel will be provided to the study participants at Visit 2 prior to self-administration. The training is designed to be representative of the instruction and training materials that will be used in the post-marketing setting. The training will consist of a walk-through of the IFU for the injection devices by the site personnel. Finally, the first actual injection will then be supervised by site personnel including feedback to the subject as needed.

6.8. Compliance with Study Treatment Administration

A record of the number of safety syringes dispensed and returned by each subject must be maintained and reconciled with study treatment and compliance records.

6.8.1. Self-Administration at the Clinic

Following the training (see Section 6.7) at Visit 2 (Week 0), the subject (and/or caregiver, if applicable) will self-administer the first dose of study treatment by SC injection under medical supervision of the investigator or designee at the study site. The subject/caregiver will also administer the dose of study treatment at the clinic under medical supervision, but without further training, at Visit 4 (Week 8). Observations about the injection will be recorded by the investigator using a checklist for the doses administered in the clinic. Details of the Observer Checklist can be found in the SRM. The subject will complete a patient diary with a visual analogue scale (VAS) indicating the pain experience immediately following, 1- and 24-hours after the dose.

The date, time of the dose, person administering the dose (subject/caregiver) and site of administration (thigh, abdomen or upper arm [caregiver only]) of each dose administered in the clinic will be recorded on the Observer Checklist and in the source documents.

Subjects will be monitored for 1 hour after mepolizumab self-administrations in the clinic at Visit 2 and Visit 4. In the event of an acute severe reaction (e.g., anaphylaxis) following administration of study treatment, there are personnel/staff onsite at the treatment facility who are appropriately trained in basic life support to manage the

subject including administration of medications (e.g., epinephrine), and have access to a system that can promptly transport the patient to another facility for additional care if appropriate.

6.8.2. Self-Administration Outside the Clinic

The subject (or caregiver) will self-administer the dose of study treatment outside the clinic and without observation during Week 4, up to 24 hours after attending clinic Visit 3. The subject/caregiver will complete a checklist of the steps required to use the safety syringe, which will also include the date and time of dose, site of injection, person administering the dose (subject/caregiver) and the ease with which the subject/caregiver was able to complete each of the critical steps required to administer the dose from the safety syringe. In addition, the subject will complete the patient diary capturing the pain experienced by the subject immediately following, 1- and 24-hours after the dose.

Subjects will be instructed to contact clinical study staff if they have concerns or questions regarding self-administration. They will have the option of returning to the clinical site for further training or assistance with self-administration. Requirement for additional training will be documented.

Compliance with the safety syringe will be assessed through reviewing the subject completed checklist, inspection of the returned safety syringe and querying the subject during the next site visit (Visit 4) and documented in the source documents.

For self-administration of mepolizumab outside of the clinic (at home), subjects should be instructed to call the investigator and/or go to an Emergency Department for any unusual symptoms (e.g. skin rash [hives] or redness, swelling of the face or mouth, becoming wheezy, coughing or having difficulty in breathing and/or feeling weak or light headed).

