Three doses of mepolizumab liquid drug product in safety syringe will be self-administered by the subject/caregiver at 4-weekly intervals; 2 doses will be administered under observation in the clinic (at Visits 2 and 4). The second in clinic administration (Visit 4) will not include any onsite training or support, other than the IFU, which could assist the subject. One dose will be administered outside the clinic and without observation (within 24 hours after attending the clinic for Visit 3). Following each injection, subjects will complete a patient diary, included in the Study Reference Manual (SRM), and report the pain experienced immediately following, 1- and 24-hours post injection. Observations about the injection will be recorded by the investigators for the doses administered in the clinic using an observer checklist. For the unobserved dose administered at home, a similar checklist detailing the steps required to successfully administer the injection will be completed by the subject/caregiver. All injections will be assessed by the investigator for success based on:

- Direct observation of the self-administration using the investigator Observer Checklist if the mepolizumab dose was administered in the clinic, and inspection of the safety syringe
- Subject/caregiver completed checklist and inspection by the investigator of the returned safety syringe if the mepolizumab dose was administered outside the clinic

A self-administered injection is considered successful if the following criteria are met:

- Use of a correct injection site (abdomen/thigh or upper arm [caregiver only])
- Full dose administered: subject fully inserts the needle, slowly depresses the plunger until the stopper reaches the bottom of the syringe and activates the needle guard by moving the thumb up
- No observations are made with respect to the safety syringe, following inspection by the investigator, which indicates the full dose has not been dispensed

If the above criteria are met, the investigator will confirm the injection was successfully delivered.

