- d. Perform prior to mepolizumab administration during the study and prior to restarting pre-study mepolizumab treatment on study completion/early withdrawal.
- e. Subjects will be instructed to contact clinical study staff at any time if they have concerns or questions regarding self-administration. They will have the option of returning to the clinical site for further training or assistance with self-administration. Requirement for additional training or assistance will be documented.
- f. Self-administration of mepolizumab using the safety syringe should occur within 24 hours following the clinic visit.
- g. Includes measurement of eosinophil levels for pharmacodynamic analysis at Visits 2, 3, 4 and 5
- h. Pharmacogenetic sample may be drawn any time after the respective informed consent form is signed and the subject is enrolled.
- i. Vital signs include temperature, sitting blood pressure, respiratory rate and pulse.
- j. Any SAEs assessed as related to study participation (e.g., study treatment, protocol-mandated procedures, invasive tests, or change in existing therapy) or related to a GSK concomitant medication, will be recorded from the time a subject consents to participate in the study up to and including any follow up contact. All other AEs/SAEs are recorded from the start of study treatment until the End of Study / Early Withdrawal visit.
- k. Injection site reactions (e.g., induration, erythema, edema, rash, pruritus, pain) are to be recorded on both AE and SAE CRF forms.
- l. Information on systemic reactions and events that meet the anaphylaxis criteria is collected on both AE and SAE CRF forms.
- m. Patient diary should be dispensed prior to administration of injection

- n. For any subject who withdraws prior to Week 12, patient diary and study drug for self-administration outside of clinic will be returned at the Early Withdrawal visit (if applicable).
- o. Assessment to be completed at the Early Withdrawal visit only if the dose of mepolizumab immediately prior to withdrawal was administered outside of the clinic.
- p. Includes both the injection outside the clinic from Week 4 and the injection in clinic at Week 8
- q. In a subset of subjects only. Completed over the telephone after the End of Study/Early Withdrawal Visit

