14.9. Appendix 9: Example Mock Shells for Data Displays

Example TAB_POP1
Protocol: MID205667
Population: All Subjects Enrolled

Page 1 of 1

Table X
Summary of Study Populations

Population	Liquid Safety Syringe (N=XX)
All Subjects Enrolled	XX
All Subjects (Safety)	XX (XX%)
Pharmacokinetic	XX (XX%)
Pharmacodynamic	XX (XX%)

userid: /arenv/arprod/compound/study/final/drivers/drivername.sas DDMMYYYY HH:MM

Example TAB_POP2
Protocol: MID205667
Population: All Subjects (Safety)

Table X
Summary of Disease Duration

		Liquid Safety Syringe (N=XX)
Duration of Disease (years)	n	XX
	>=1 to <5	XX (XX%)
	>=5 to <10	XX (XX%)
	etc.	XX (XX%)
	Mean	XX.X
	SD	XX.XX
	Median	XX.X
	Minimum	XX
	Maximum	XX

userid: /arenv/arprod/compound/study/final/drivers/drivername.sas DDMMYYYY HH:MM

Example TAB_EX1
 Protocol: MID205667
 Population: All Subjects (Safety)

Table X
 Summary of Injection Site

Visit	Injection Site	Liquid Safety Syringe (N=XX)
WEEK 0	n	XX
	Abdomen	XX (XX%)
	Upper arm	XX (XX%)
	Thigh	XX (XX%)
	Other, or intervention required	XX (XX%)
WEEK 4	n	XX
	Abdomen	XX (XX%)
	Upper arm	XX (XX%)
	Thigh	XX (XX%)
	Other	XX (XX%)
WEEK 8	n	XX
	Abdomen	XX (XX%)
	Upper arm	XX (XX%)
	Thigh	XX (XX%)
	Other, or intervention required	XX (XX%)

userid: /arenv/arprod/compound/study/final/drivers/drivername.sas DDMMYYYY HH:MM

Example TAB_POP3
Protocol: MID205667
Population: All Subjects (Safety)

Table X
Summary of Prior Experience with Self-Injection of Medication

Visit		Liquid Safety Syringe (N=XX)
	Does the subject have any prior experience with self-injection of medication?	XX
	No	XX (XX%)
	Yes	XX (XX%)
	Autoinjector (Pen)	XX (XX%)
	Prefilled syringe	XX (XX%)
	Vial and syringe	XX (XX%)
	Other method	XX (XX%)

userid: /arenv/arprod/compound/study/final/drivers/drivename.sas DDMMYYYY HH:MM

Example TAB_POP4
 Protocol: MID205667
 Population: All Subjects (Safety)

Table X
 Summary of Baseline Mepolizumab Use

		Liquid Safety Syringe (N=XX)
Is the subject currently receiving treatment with mepolizumab?	n	XX
	No	XX (XX%)
	Yes	XX (XX%)
Blood eosinophil count criteria met [1][2]?	n	
	No	XX (XX%)
	Yes	XX (XX%)
Most recent blood eosinophil count prior to starting mepolizumab (cells/uL) [2]	n	XX
	Median	XX.X
	Minimum	XX
	Maximum	XX

[1] Blood eosinophil count immediately before starting mepolizumab that was ≥ 150 cells/uL or a blood eosinophil count that was ≥ 300 cells/uL in the 12 months prior to starting mepolizumab.

[2] Subjects currently receiving treatment with mepolizumab only.

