[3] Subject / caregiver was not able to (or did not) complete task after multiple attempts and reference to the IFU, or intervention was required.

userid: /arenv/arprod/compound/study/final/drivers/drivername.sas DDMMYYYY HH:MM

Example TAB_INJ3 (cont.)
 Protocol: MID205667
 Population: All Subjects (Safety)

Table X.X
 Summary of Observer Checklist for In-Clinic Injections

Visit: WEEK 0

		Liquid Safety Syringe (N=XX)
Check that the subject / caregiver begins to push the plunger slowly down.	n	XX
	Easily [1]	XX (XX%)
	With some difficulty [2]	XX (XX%)
	Did not complete [3]	XX (XX%)
Check that the subject / caregiver continues to push the plunger all the way down until the stopper reaches the bottom of the syringe and all of the solution is injected.	n	XX
	Easily [1]	XX (XX%)
	With some difficulty [2]	XX (XX%)
	Did not complete [3]	XX (XX%)
Check that the subject / caregiver moves thumb up, allowing the plunger to rise to activate the needle guard.	n	XX
	Easily [1]	XX (XX%)
	With some difficulty [2]	XX (XX%)
	Did not complete [3]	XX (XX%)

[1] Subject / caregiver completed task easily without repeated reference to the IFU.

[2] Subject / caregiver completed task but with some difficulty or repeated reference to the IFU for assistance.

[3] Subject / caregiver was not able to (or did not) complete task after multiple attempts and reference to the IFU, or intervention was required.

userid: /arenv/arprod/compound/study/final/drivers/drivename.sas DDMMYYYY HH:MM

Programming Note: Continue for Week 8.

Example TAB_INJ4
 Protocol: MID205667
 Population: All Subjects (Safety)

Table X.X
 Summary of Subject Completed Checklist for At-Home Injection at Week 4

		Liquid Safety Syringe (N=XX)
User who logged in to complete the at-home injection checklist."	n	XX
	Patient	XX (XX%)
	Caregiver	XX (XX%)
Time from removal of syringe from storage to injection (mins)	n	XX
	Mean	XX.X
	SD	XX.XX
	Median	XX.X
	Minimum	XX
	Maximum	XX
Did you need to contact the investigator / site prior to the injection for additional training?	n	XX
	Yes - Telephone	XX (XX%)
	Yes - Clinic Visit	XX (XX%)
	No	XX (XX%)
Was the safety syringe stored in the fridge at 2-8 degrees C before preparing for use?	n	XX
	Yes	XX (XX%)
	No	XX (XX%)

- [1] I was able to complete the task easily without repeated reference to the IFU.
- [2] I was able to complete the task but with some difficulty or repeated reference to the IFU for assistance.

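### Does the SAP need a rule for a Week 4 dose taken at the site or with staff help?

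*Protocol*

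**What the plan says.** **Return to the site.** Protocol 6.8.2 plans the second dose away from the clinic, unobserved, within 24 hours of Visit 3. It then adds for subjects with concerns: "They will have the option of returning to the clinical site for further training or assistance with self-administration".

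**Documentation.** The same paragraph ends: "Requirement for additional training will be documented". Footnote e to the Time and Events Table (Protocol 7.1, copied in SAP 14.1.1) is wider: "Requirement for additional training or assistance will be documented".

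**Display.** The SAP shell for the home checklist (TAB_INJ4, Appendix 9) asks "Did you need to contact the investigator / site prior to the injection for additional training", and one of its answers is "Yes - Clinic Visit". It has no row for place of dosing or for help during the injection. The injection-site shell (TAB_EX1) has the category "Other, or intervention required" at Weeks 0 and 8, but only a plain Other at Week 4.

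**Form.** Protocol 4.1 ties the method of assessment to the place of dosing: "Direct observation of the self-administration using the investigator Observer Checklist if the mepolizumab dose was administered in the clinic". Protocol 6.8.1 likewise has the dosing details "of each dose administered in the clinic will be recorded on the Observer Checklist and in the source documents". The schedule places that checklist at Visits 2 and 4 only.

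**Endpoint.** Protocol 3 and SAP 2.2 describe the Week 4 endpoint as the unobserved dose away from the clinic. In SAP 7.2 the denominator is everyone who attempts the Week 4 injection, with no condition on place or help.

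**The concern.** Week 4 is the only dose meant to show that subjects or caregivers can manage alone. A dose injected at the site with staff at hand is not evidence of that. Yet nothing in SAP 7.2 says whether such a dose is a success, a non-success or out of the analysis.

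The form could also affect the result. On the Observer Checklist a step that needed intervention falls in the same category as a step not completed. The home checklist has no such category. A helped dose could therefore be graded differently depending on which form was used.

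At stake are the secondary endpoint and the two combined rates that include Week 4 (Weeks 4 and 8; all three doses). If the rule were chosen after the data were seen, it could be chosen to flatter the device.

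**Working it through.** **1. Do the passages contradict each other?**

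| Topic | One text | Other text | Can both be followed? |
|---|---|---|---|
| What is documented | Protocol 6.8.2: training | Footnote e: training or assistance | Yes. A site that follows footnote e also satisfies 6.8.2. |
| Form for a clinic dose | Protocol 4.1 and 6.8.1: Observer Checklist | Protocol 7.1 and 7.3: Observer Checklist at Visits 2 and 4 | Yes. Visits 2 and 4 are the planned clinic doses. |
| Form at Week 4 | Protocol 7.1: subject/caregiver checklist | Protocol 7.3: that checklist applies when the dose is taken outside the clinic | Yes, for the planned home dose. A clinic dose at Week 4 is not covered. |

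The first row is a difference of scope. The others agree on the planned doses and are silent on an unplanned one.

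**2. Is the unplanned case in the documents?** Not expressly. Protocol 6.8.2 calls for dosing outside the clinic, and Protocol 7 rules out waivers except for immediate safety concerns. Retraining at the site followed by a home injection satisfies the return option in full, and that dose is an ordinary Week 4 attempt.

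**3. If it did occur, what does the text give?** The subject attempted a Week 4 injection, so SAP 7.2 keeps the subject in the denominator. Success is the investigator's judgement under the three criteria of Protocol 4.1: injection site, full dose and syringe inspection. None of them depends on setting. The event could also surface through the Visit 4 query recorded in source documents (Protocol 6.8.2), and through the deviation tracking of SAP 4.1 if judged important.

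**4. How far could the reading matter?** Inputs: n = 50 (Protocol 9.2.2) and exact Clopper-Pearson 95% limits (SAP 7.1). The number k of Week 4 doses that were rated successful but taken at the site or with help is an assumption; the documents give none.

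For x successes in n, the lower limit is the 0.025 quantile of Beta(x, n−x+1) and the upper limit is the 0.975 quantile of Beta(x+1, n−x).

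The plan's own table comes first. 35/50 gives 55.39 to 82.14 (stated 55, 82), and 48/50 gives 86.29 to 99.51 (stated 86, 100). All 11 rows reproduce after rounding.

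The three readings, with 48 of 50 rated successful:

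| k | Counted as success, x/n | Kept in denominator only, (x−k)/n | Left out, (x−k)/(n−k) |
|---|---|---|---|
| 0 | 48/50 = 96.0% (86.3–99.5) | same | same |
| 1 | 48/50 = 96.0% (86.3–99.5) | 47/50 = 94.0% (83.5–98.7) | 47/49 = 95.9% (86.0–99.5) |
| 2 | 48/50 = 96.0% (86.3–99.5) | 46/50 = 92.0% (80.8–97.8) | 46/48 = 95.8% (85.7–99.5) |
| 3 | 48/50 = 96.0% (86.3–99.5) | 45/50 = 90.0% (78.2–96.7) | 45/47 = 95.7% (85.5–99.5) |

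Removal from the numerator costs k/n, which is 1/50 = 2 points per dose at any base rate.

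Leaving doses out costs x/n − (x−k)/(n−k) = k(n−x)/[n(n−k)], which depends on the base rate. For k = 3:

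- x = 48: 3×2/(50×47) = 6/2350 = 0.26 points
- x = 40: 3×10/2350 = 1.28 points (37/47 = 78.7% against 80%)
- x = 35: 3×15/2350 = 1.91 points (32/47 = 68.1% against 70%)

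So leaving doses out is harmless near 96% but not at every success rate in the plan's table.

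**The case for a change.** The best argument for a change is that assistance is named separately from training, and footnote e is attached to the Week 4 home-dose row. A helped injection is therefore a fair reading of the text. The protocol itself treats support as material, since it withholds everything except the Instructions for Use at the Visit 4 dose. The displays would not reveal the case either: TAB_INJ4 stops at contact before the injection, and the listing of who injected takes the Week 4 entry from the eDiary login. A sentence written before database freeze would cost little and would remove a choice made after seeing the data.

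Much of this stands as description. Footnote e and 6.8.2 do differ in scope, SAP 7.2 is silent, and a reader who takes the unobserved label as a condition of success could reach a different count.

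The rest is weaker. The three readings are not equally supported. Leaving out an attempted dose goes against the SAP's stated denominator, and refusing it as a success adds a criterion that Protocol 4.1 does not list. The evidence on what is recorded comes from example shells, which are not an inventory of the data collected: TAB_INJ2 still lists autoinjector errors in a safety-syringe study. The actual checklists are in the Study Reference Manual, which the two documents do not reproduce and which may record more.

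**Conclusion.** No change follows. This is missing detail about an unplanned case; no stated rule or figure is shown to be wrong. The passages on documentation and forms are compatible for every planned dose. For a Week 4 dose taken at the site, the literal reading gives a workable answer: it is an attempt, judged by the same success criteria as any other. Should such doses occur, an analyst can note their number when reporting the Week 4 rate.

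The effect is 2 points per dose at n = 50 under the strictest reading. For three doses left out it is about 0.3 to 1.9 points over base rates from 96% down to 70%. These sizes assume 50 Week 4 attempts and an invented k; at k = 0 all readings coincide. The combined rates could move with the Week 4 result. The Week 8 primary rate cannot, and the study is descriptive with no hypothesis test.
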